11.2 Serious Adverse Events (SAE) (Appendix J)

A serious adverse event is any adverse drug experience occurring at any dose that results in any of the following outcomes:

- Death.
- A life-threatening adverse drug experience – any adverse experience that places the patient, in the view of the initial reporter, at immediate risk of death from the adverse experience as it occurred. It does not include an adverse experience that, had it occurred in a more severe form, might have caused death.
- Inpatient hospitalization or prolongation of existing hospitalization.
- A persistent or significant disability/incapacity – a substantial disruption of a person's ability to conduct normal life functions.
- A congenital anomaly/birth defect.

Important medical events that may not result in death, be life-threatening, or require hospitalization may be considered a serious adverse drug experience when, based upon appropriate medical judgment, they may jeopardize the patient or subject and may require medical or surgical intervention to prevent one of the outcomes listed in this definition. Examples of such medical events include allergic bronchospasm requiring intensive treatment in an emergency room or at home, blood dyscrasias or convulsions that do not result in inpatient hospitalization, or the development of drug dependency or drug abuse (21 CFR 312.32).

Important medical events as defined above, may also be considered serious adverse events. Any important medical event can and should be reported as an SAE if deemed appropriate by the PI or the IND Sponsor, The University of Texas MD Anderson Cancer Center Institutional Review Board system (UTMDACC IRB) .

All events occurring during the conduct of a protocol and meeting the definition of a SAE must be reported to the IRB in accordance with the timeframes and procedures outlined in "The University of Texas MD Anderson Cancer Center Institutional Review Board Policy on Reporting Serious Adverse Events". Unless stated otherwise in the protocol, all SAEs, expected or unexpected, must be reported to UTMDACC IRB, regardless of attribution (within **5 working days** of knowledge of the event).

All life-threatening or fatal events, expected or unexpected, and regardless of attribution to the study drug, require a written report to be submitted within **24 hours** (next working day) of knowledge of the event to the Safety Project Manager in UTMDACC IRB .

The MD Anderson "Internal SAE Report Form for Prompt Reporting" will be used for reporting to UTMDACC IRB .

SAEs will be captured from the time the patient signs consent until 30 days after the last dose of drug. Serious adverse events must be followed until clinical recovery is complete and laboratory test have returned to baseline, progression of the event has stabilized, or there has been acceptable resolution of the event.

Additionally, any SAE that occurs after the 30-day time period and that is related to the study treatment must be reported to UTMDACC IRB. This may include the development of a secondary malignancy.

It is the responsibility of the PI and the research team to ensure that SAEs are reported according to the Code of Federal Regulations, Good Clinical Practices, the protocol guidelines, the sponsor's guidelines, and Institutional Review Board policy.

12.0 Criteria for Removal from the Study

12.1 Patients will be taken off study if these values are met or exceeded:

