4.2 Armodafinil Common Adverse Reactions

Most commonly reported adverse reactions: headache, nausea, dizziness, and insomnia

- 4.21 Occurring in greater than >10% of study subjects across randomized studies with armodafinil:

Central nervous system: Headache (14% to 23%)

- 4.22 Occurring in 1% to 10% of study subjects across randomized studies with armodafinil:

Cardiovascular: Palpitation (2%), increased heart rate (1%)

Central nervous system: Dizziness (5%), insomnia (4% to 6%; dose related), anxiety (4%), depression (1% to 3%; dose related), fatigue (2%), agitation (1%), attention disturbance (1%), depressed mood (1%), migraine (1%), nervousness (1%), pain (1%), pyrexia (1%), tremor (1%)

Dermatologic: Rash (1% to 4%; dose related), contact dermatitis (1%), hyperhidrosis (1%)

Gastrointestinal: Nausea (6% to 9%; dose related), xerostomia (2% to 7%; dose related), diarrhea (4%), abdominal pain (2%), dyspepsia (2%), anorexia (1%), appetite decreased (1%), constipation (1%), loose stools (1%), vomiting (1%)

Genitourinary: Polyuria (1%)

Hepatic: GGT increased (1%)

Neuromuscular & skeletal: Paresthesia (1%)

Respiratory: Dyspnea (1%)

Miscellaneous: Flu-like syndrome (1%), thirst (1%)

- 4.23 Postmarketing and/or case reports: Anaphylactoid reaction, angioedema, hypersensitivity, liver enzymes increased, pancytopenia, systolic blood pressure increased (see section on Serious adverse events for symptom drug below)

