5.0 Study Design

Using a Phase II blinded, randomized placebo-controlled trial, with optional open label extension period, we will evaluate armodafinil's ability to reduce patient-reported fatigue in patients with treated head and neck cancer. This type of trial design is especially important in trials where symptom reduction is the outcome and where knowledge of the treatment arm might bias assessment by the staff or patient. We will purchase commercial grade drug and matching placebo to be dispensed by the investigational pharmacy.

Design: Phase II blinded, randomized placebo-controlled trial, with optional open label extension period

Symptom Intervention Agent: Armodafinil

Study Period: 8-12 weeks depending on participation in the optional open label component : intervention agent daily for 4 weeks (Part I), with continued assessment follow-up period of 4 weeks (Part II). At the end of the 4-week agent intervention, the patient will be given the option to receive open label armodafinil during the 4 weeks follow-up period. If the patient agrees to this option, the follow-up period for these patients will be extended for another 4 weeks.

Primary Symptom Outcome Variable: 4-week (+/- 7 days) area under the curve (AUC) for patient-reported fatigue at its worst (item from the Brief Fatigue Inventory).

Secondary outcomes assessed will include: (1) the 5 most-severe MDASI-HN symptoms at 2-month follow up based on previously collected MDASI-HN data (2) overall MDASI-HN symptom severity, (3) overall MDASI-HN interference, (4) patient-reported alertness (via Epworth Sleepiness Scale), and (5) work productivity and activity impairment questionnaire.

Forty patients will be randomized to either armodafinil or placebo, twenty in each arm. AUC values for patients who drop out of the study after providing 2 weeks of AUC data will be included by carrying their last symptom data forward for the remaining study period under the intent-to-treat rule. The carry-forward method of handling drop-outs will be revisited upon completion of the study to determine if adjustments to these values can be made using longitudinal regression models estimated from patients who completed the entire study.

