12.11 Alkaline phosphatase (ALP) is 2 times the upper limit of normal

12.12 Aspartate aminotransferase (AST) or alanine aminotransferase (ALT) is 2 times the upper limit of normal

- 12.13 Total bilirubin >1.5 x ULN
- 12.14 Signs and symptoms of severe rash (CTC version 4 \geq grade 3) or hypersensitivity
- 12.15 Pregnancy during the study period
- 12.16 INR > 1.5. Treating physician notified so that medical management occurs.
- 12.17 Development of psychosis.
- 12.18 Development of symptomatic tachycardia or palpitations or uncontrolled hypertension.

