13.23 Non-Compliance with Study Agent

Patients who do not comply with study agent dosing requirements will remain in the study under the intent-to-treat rule.

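### Section 12 takes patients off study for events that include listed armodafinil reactions, and no fatigue follow-up is stated, so avoidable gaps in the primary outcome may fall unevenly between arms

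*Combined protocol and SAP*

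**What the plan says.** Section 12.0 is about leaving the study, not only about stopping the drug: "Patients will be taken off study if these values are met or exceeded". The criteria listed under it include "Aspartate aminotransferase (AST) or alanine aminotransferase (ALT) is 2 times the upper limit of normal", "Signs and symptoms of severe rash" at CTC grade 3 or above (or hypersensitivity), and "Development of symptomatic tachycardia or palpitations or uncontrolled hypertension". The others are ALP, bilirubin, INR, pregnancy and psychosis.

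Several of these overlap with reactions the protocol lists for armodafinil. Section 4.2 gives palpitation 2% and increased heart rate 1%, and mentions hypersensitivity, raised liver enzymes and raised systolic pressure as postmarketing or case reports without rates. Section 4.3 gives rash in 2% on armodafinil against 0% on placebo (1% at 150 mg), and small, consistent rises in blood pressure and pulse.

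Three other places bear on what happens next:

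- Section 13.23: "Patients who do not comply with study agent dosing requirements will remain in the study under the intent-to-treat rule".
- Section 5.0 advises patients to stop the drug as soon as a body rash appears and to tell study staff. It does not mention leaving the study.
- Section 5.0 also says that AUC values for patients who drop out after two weeks of data "will be included by carrying their last symptom data forward for the remaining study period". Section 13.2 (Intent to treat) replaces anyone who drops out earlier.

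**The concern.** A patient who merely skips doses is followed and analysed as randomized. A patient who meets a Section 12 criterion leaves the study, and nothing in the supplied text says that the BFI is still collected. The plan itself therefore creates missing primary data in patients who could often still answer a telephone item. Because several criteria are listed armodafinil reactions, those gaps may be more common in the active arm.

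The analysis then fills the gap with the last score, or the patient is replaced. Replacement is the more serious of the two, because it takes a randomized patient out of the comparison on the basis of something that happened after randomization. Section 13 presents the trial as a source of effect-size and variability estimates for a larger study, and each patient is 1/20 = 5% of an arm, so avoidable losses matter even when few are expected.

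**Working it through.** **The plan's own figure.** Section 13.1 states 20 per arm, 0.70 SD, one-sided 5% and 70% power. The normal approximation gives 71.5% and the noncentral t gives 70.2%, so the figure reproduces. The same section equates 0.70 SD with 1.7 points, which implies an SD of 1.7/0.70 = 2.43 points.

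**How many removals.** The documents give no rate for meeting a Section 12 criterion. They give any-grade rates: rash 1% at 150 mg (Section 4.3; 150 mg is the highest daily dose in Section 6.0) and palpitation 2% (Section 4.2). I take 1% (rash alone) to 3% (1% + 2%). For these two events the range is an upper guide, because Section 12 requires severe rash or symptomatic events. Criteria without a rate are left out.

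- Expected removals among 20: 20 × 0.01 = 0.2; 20 × 0.03 = 0.6.
- Chance of at least one, 1 − (1 − p)^20: 1 − 0.99^20 = 18%; 1 − 0.97^20 = 46%.
- Chance of two or more: about 2% and 12%.
- Sensitivity: adding increased heart rate (1%) gives 4%, 0.8 expected removals and a 56% chance of at least one.

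**How much of the AUC is missing.** On the 4-week AUC of Section 5.0, removal at day 14 leaves (28 − 14)/28 = 50% to be carried forward, and removal at day 21 leaves (28 − 21)/28 = 25%. Section 13.21 describes eight weeks of scores. If that governs, removal at day 14 leaves (56 − 14)/56 = 75%.

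**Shift in the arm mean.** Let k active patients be carried forward or replaced, each with an AUC wrong by g SD. The shift is (k/20) × g SD, or (k/20) × g × 2.43 points. The value of g is an assumption, taken as 0.35 to 1.0.

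| k | g = 0.35 | g = 1.0 |
|---|---|---|
| 1 | 0.0175 SD = 0.04 points | 0.05 SD = 0.12 points |
| 2 | 0.035 SD = 0.09 points (0.085) | 0.10 SD = 0.24 points |

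Against 1.7 points (0.70 SD) this runs from 0.0175/0.70 = 2.5% to 0.10/0.70 = 14%. The upper end is demanding for carry-forward alone. At day 14 only half of a 4-week AUC is imputed, so an error of 1.0 SD (2.43 points) in the average needs the carried scores to be off by 2.43/0.5 = 4.9 points. Even 0.35 SD (0.85 points) needs 0.85/0.5 = 1.7 points.

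**Averaged over the chance of removal.** From (0.2/20) × 0.35 × 2.43 = 0.01 points to (0.6/20) × 1.0 × 2.43 = 0.07 points.

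**Effect on the test, if the error happened to favour armodafinil.** The one-sided type I error is 1 − Φ(1.645 − b/√(1/20 + 1/20)), with b the shift in SD. It rises from 5% to 5.6–6.9% for one patient and 6.3–9.2% for two. If the error ran the other way, it would fall below 5%.

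**Power.** With one or two active patients contributing no AUC, power is 69.1% or 68.0% (t), against 70.2%. Loss of power is not the issue.

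**The case against.** The case for leaving the text alone is mainly about size, and much of it stands.

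- **Few removals.** At 1% to 3%, the chance of no active-arm removal is 82% to 54%. Section 8.2 already excludes many patients at risk. Section 7.15 plans no study-specific laboratory tests beyond baseline liver function, so the liver and INR criteria depend on tests done for clinical reasons.
- **The trial stopping rule.** Under Section 5.0, one armodafinil-related grade 3 or 4 toxicity in the active arm ends the study. A related grade 3 rash there would not act as a single dropout.
- **Milder rash.** Section 5.0 handles it by stopping the drug, and it need not reach Section 12.
- **Appendix X.** The assessment schedule is not in the supplied text, so assessments after removal cannot be ruled out.

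Two stronger readings are tempting and are not supported. A reader might infer that data stop only in the active arm. The criteria apply to both blinded arms, some (pregnancy, for example) are not listed drug reactions, and rash is the only listed reaction with a placebo rate. A reader might also infer that the gaps favour armodafinil. That requires later fatigue to be worse than the last score. Patients enter with worst fatigue of 5 or more, so scores may fall over time; carrying forward an earlier, higher score would then count against the arm with more removals. A patient who tolerates the drug badly may also leave with a high score.

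What survives is that the rules differ for patients who stop dosing for different reasons, and that the resulting data loss is avoidable.

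**Conclusion.** The concern holds in a limited form. As written, the plan removes patients from the study for events that overlap with listed armodafinil reactions, states no fatigue assessment afterwards, and keeps other patients who stop dosing. Sections 5.0, 12.0, 13.2 and 13.23 do not form one consistent rule, and replacing early dropouts departs from the stated intent-to-treat principle.

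The likely number affected is 0.2 to 0.6 of 20 active patients. If one or two are affected, the arm mean moves by about 0.04 to 0.24 points, in either direction. This rests on any-grade rates standing in for Section 12 events, on an assumed error of 0.35 to 1.0 SD per affected patient, on no offsetting removals in the placebo arm, and on Appendix X not already providing for follow-up. It does not threaten the trial's conclusion by itself. The case for changing it is that the missing data are created by the plan and are cheap to prevent.

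**What to change.** Leave the Section 12 criteria and all clinical management as they are. The change concerns data collection and analysis only.

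1. State in Section 12 that the BFI and other patient-reported assessments continue on schedule for every randomized patient who meets a criterion, unless the patient withdraws consent or is unable to respond. Section 7.1 already allows phone, IVR and mail.
2. State in Section 13 that these observed scores enter the primary AUC in the arm to which the patient was randomized.
3. Reconcile the rash instruction in Section 5.0, removal in Section 12.0, replacement in Section 13.2 and the non-compliance rule in Section 13.23, so that a patient who meets a Section 12 criterion in the first two weeks is not replaced out of the primary comparison. Bring Appendix X into line.

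The cost is protocol wording and a few extra contacts. Section 11.1 already has staff phoning weekly, and Section 11.2 captures serious adverse events until 30 days after the last dose. Some scores will reflect time off drug, which the intent-to-treat rule in Section 13.23 already accepts.

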12.11 Alkaline phosphatase (ALP) is 2 times the upper limit of normal

12.12 Aspartate aminotransferase (AST) or alanine aminotransferase (ALT) is 2 times the upper limit of normal

- 12.13 Total bilirubin >1.5 x ULN
- 12.14 Signs and symptoms of severe rash (CTC version 4 \geq grade 3) or hypersensitivity
- 12.15 Pregnancy during the study period
- 12.16 INR > 1.5. Treating physician notified so that medical management occurs.
- 12.17 Development of psychosis.
- 12.18 Development of symptomatic tachycardia or palpitations or uncontrolled hypertension.

13.0 Statistical Analysis Plan

13.1 Sample Size and Randomization

Forty patients will be randomized equally to the 2 treatment arms - armodafinil and placebo. With 20 patients per treatment arm, we will be able to detect a 0.70 SD effect size on the BFI AUC between the 2 treatments with 70% power and one-sided 5% significance test. A 0.70 effect size for the BFI is about **1.7 points (change in terms of AUC)** on a 0 to 10 scale. Because this is a small Phase II study with the intent of providing effect size estimates to inform a large clinical trial in the future, we chose a modest statistical power.

13.2 Analysis Plan

We will test armodafinil in its ability to reduce values of patient- reported fatigue scores. Our emphasis is to test the efficacy of armodafinil as a potential agent in reducing patient-reported symptoms in patients with HNC after planned cancer therapy. The proposed phase II clinical trial for screening this potentially effective symptom-intervention agent will provide moderate power in detecting modest intervention effect. If the treatment has a more pronounced effect, it will be detected with higher power.

This study will allow us to obtain estimates of treatment effect and the variability of these estimates. Estimates of treatment effect will be obtained using standard linear regression techniques in which AUC values ($hn(i)$) are regressed on indicator variables that represent treatment received. Estimates of treatment effect and between-subject variability will then be used to design a more comprehensive study in future clinical trials.

In addition to the formal evaluation of treatment effects on the primary outcome, we will also examine the prognostic effects of disease stage, type of cancer treatment, ECOG status, age and gender in predicting the outcome variable. We will compare the percentages of patients who were satisfied with the study drug against those who were taking the placebo. We will include an indicator variable in our model to determine whether patients who had a full dose of armodafinil differ from those who had a run-in period. Standard exploratory data analysis techniques and descriptive statistics will be used.

Assuming that patients accrue at the rate of 4 per month, we anticipate that this pilot study will require approximately 14 months to complete.

Intent to treat

We will need at least 2 weeks of BFI data for the patient to calculate AUC. Any patient who drops out prior to this will be replaced.

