7.0 Data Collection Tools

7.1 Symptom Measurement Patient-reported symptom data will be collected using the: (1) **Brief Fatigue Inventory (BFI)**; (2) **MDASI-HN** module of the M. D. Anderson Symptom Inventory (Appendix F and E) and (3) **Epworth Sleepiness Scale (ESS)** (Appendix G). These and other patient-reported outcome questionnaires will be completed face-to-face in the clinic at the time of enrollment. Subsequent assessments during the study period will be collected either face to face in the clinic, through phone calls by field coordinators or study staff, by Interactive Voice Response (IVR) system, or by regular mail, as outlined in the Assessment Schedule (Appendix X).

Interactive Voice Response (IVR) system combines the use of touch-tone telephones with computers and the Internet to follow patients who have symptoms like pain that need to be monitored closely while away from the hospital. Using the telephone keypad, of a touch-tone telephone, a patient rates his/her pain at its worst in the past 24 hours from 0 (no pain) to 10 (pain as bad as you can imagine). Even when the patient responds using the keypad, these systems are referred to as interactive voice response (IVR) systems. An IVR system should be especially helpful for assessing symptoms such as pain, fatigue, distress, or sleep disturbance that patients may be reluctant to report to their treatment team. The IVRS is programmed to contact patients at their preferred times on specified dates. Once a contact is made, the symptom assessment script runs. Patient responses to the symptom and interference questions are deposited into a web-based database with real-time updates. Brochure describing how to report symptoms through the IVRS will be provided to patients who choose to use it (Appendix HH).

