8.2 Exclusion Criteria

8.21 Patients who rated their fatigue level at 4 or less over the past 24 hours based on the fatigue at its worst item of the BFI.

8.22 Patients with clinical evidence of active persistent cancer or progressive disease after completing planned cancer therapy, or with active recurrent cancer.

8.23 Patients with potential medical or other underlying causes of fatigue, as determined by the treating physician or PI.

8.24 Patients with Hb <10.5 g/dL within previous 2 weeks.

8.25 Patients with untreated or uncontrolled hypothyroidism, or TSH $>$ ULN or free T4 $<$ lower level of normal within previous 2 weeks.

8.26 Patients with underlying cardiac or pulmonary disease resulting in dyspnea, hypoxia, or hypercapnea.

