The study will accrue 40 patients who will be randomized into 2 arms (armodafinil and placebo), with 20 patients each (see Section 5.0 Study Design). Prior to accruing the first patient, a randomization list will be generated by our biostatistician collaborator from the Department of Biostatistics for all 40 patients, stating to which group a patient was randomized. This list containing the accrual number and treatment group information will be given to Investigational Pharmacy. A sealed backup list will be kept by the assigned data analyst in the Department of Symptom Research. This list will be opened only if unblinding is needed.

Once a patient is enrolled, study staff will inform the Investigational Pharmacy of the patient's accrual number and patient ID. Once a patient is randomized to a treatment arm, the Investigational Pharmacy will retrieve the randomized treatment arm information from the generated randomization list and will relay that information to the dispensing Pharmacy. The patient may visit the most convenient outpatient pharmacy to pick up the study medication assigned.

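### The primary AUC model leaves out baseline BFI worst fatigue, which is recorded for every patient, so the analysis is likely less precise than it could be

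*Combined protocol and SAP*

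**What the plan says.** The primary analysis in section 13.2 is a linear regression in which the AUC values "are regressed on indicator variables that represent treatment received". Separately from that formal evaluation, the section will examine the "prognostic effects of disease stage, type of cancer treatment, ECOG status, age and gender in predicting the outcome variable". Baseline fatigue is not on this list. Section 13.2 also mentions an indicator separating full dosing from a run-in period; that is a dosing term, not a baseline covariate. Sections 13.21 to 13.23 add no baseline adjustment of the primary outcome.

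The randomisation in section 9.0 does not balance baseline fatigue either. It says that "a randomization list will be generated by our biostatistician collaborator from the Department of Biostatistics for all 40 patients", and no strata are described.

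The baseline value will nevertheless exist for everyone. Section 7.1 names the BFI first among its symptom instruments and says: "These and other patient-reported outcome questionnaires will be completed face-to-face in the clinic at the time of enrollment". Exclusion 8.21 removes patients scoring 4 or less in the past 24 hours, "based on the fatigue at its worst item of the BFI". That item is the one from which the primary AUC is built.

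On purpose, section 13.2 says: "Estimates of treatment effect and between-subject variability will then be used to design a more comprehensive study".

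**The concern.** The pre-treatment score on the outcome item is the obvious candidate predictor of its later AUC, and it costs nothing extra to collect. Leaving it out has two consequences.

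- **The estimate from this one trial.** With 20 patients per arm and no stratification, the arms can differ in baseline fatigue by chance. The unadjusted estimate is right on average over all randomisations. In the trial that is actually run, part of the baseline difference passes into the estimated effect. A baseline covariate removes the linear part of it and usually adds some power.
- **The planning inputs.** The trial is meant to supply an effect estimate and a between-subject SD. The unadjusted SD is the right input for a later trial analysed without adjustment. A later trial analysed with baseline adjustment also needs the adjusted SD, which the plan does not promise.

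Timing matters too. If adjustment is considered only after an imbalance has been seen, the choice is driven by the data.

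**Working it through.** **Inputs from the documents (section 13.1 unless noted).** 20 per arm; effect 0.70 SD; one-sided 5% test; stated power 70%; 0.70 SD equated to about "1.7 points (change in terms of AUC") on the 0 to 10 scale. The implied AUC SD is 1.7/0.70 = 2.43 points. Exclusion 8.21 limits the entry score to 5–10.

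**Not in the documents, so assumed.** The correlation r between baseline score and AUC, and the SD of the baseline score.

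**1. Reproduce the plan's power.** Noncentrality = 0.70/√(2/20) = 2.214. With 38 df and a one-sided 5% test, power is 70.2% (71.5% by the normal approximation). The stated 70% is therefore the power of the unadjusted comparison, and it is correct.

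**2. A plausible range for r.** If entry scores were uniform on the six integers 5 to 10, their SD would be √(35/12) = 1.71; a more concentrated distribution might give 1.2. Since r = slope × SD(baseline)/2.43, assumed slopes of 0.4 to 0.6 give r from 0.4 × 1.2/2.43 = 0.20 to 0.6 × 1.71/2.43 = 0.42.

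**3. Power with the covariate.** Adjustment multiplies the variance of the arm difference by 1 − r². Estimating the slope when the arms differ by chance multiplies it by about 1 + 1/36 = 1.028. One df is lost, leaving 37. The unadjusted standard error (SE) is 2.43 × √(2/20) = 0.768 points.

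| Assumed r | (1 − r²) × 1.028 | SE (points) | Power at 0.70 SD | Adjusted SD, 2.43√(1 − r²) |
|---|---|---|---|---|
| unadjusted | 1 | 0.768 | 70.2% | 2.43 |
| 0 | 1.028 | 0.779 | 69.1% | 2.43 |
| 0.2 | 0.987 | 0.763 | 70.6% | 2.38 |
| 0.3 | 0.935 | 0.743 | 72.6% | 2.32 |
| 0.4 | 0.863 | 0.714 | 75.6% | 2.23 |
| 0.5 | 0.771 | 0.674 | 79.7% | 2.10 |

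Break-even is at r of about 0.165. A simulation of 60,000 trials per setting agreed with these powers to within 0.1 to 0.2 points. It put the one-sided type I error at 4.8% to 5.1% for both tests.

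**4. Effect of a chance imbalance.** Given a baseline difference of one SE, the unadjusted estimate shifts by an expected r × 2.43 × √(2/20) = r × 0.768 points:

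- r = 0.2: 0.15 points, 9% of 1.7
- r = 0.3: 0.23 points, 14%
- r = 0.4: 0.31 points, 18%

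The one-sided error given that imbalance is 1 − Φ((1.645 ∓ r)/√(1 − r²)). At r = 0.3 this is 1 − Φ(1.345/0.954) = 7.9% if the imbalance favours armodafinil, and 1 − Φ(1.945/0.954) = 2.1% if it favours placebo. Over all possible imbalances the error is 5%.

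**5. Raw AUC or change.** Section 13.1 speaks of change, while section 13.2 models the AUC itself. With baseline in the model, and AUC averaged over a common window, subtracting baseline from the outcome alters only the baseline slope (by −1). The arm coefficient is identical.

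**The case against.** The strongest case is that this is an optional refinement. The plan's power and error level are correct, section 13.1 chose modest power on purpose for a small phase II study, and the benefit may be slight. At r = 0.2, 0.3 and 0.4 the adjusted analysis is worth about 0.3, 1.4 and 3.2 extra patients per arm (20 divided by the variance factor, less 20), and at r = 0 it costs a little. The error rate given one observed imbalance is not the criterion the plan adopts, and the adjusted SD could be computed later from the stored data. Most of this stands as a limit on the size of the concern. In particular, the 7.9% is not inflation of the trial's error rate. It does not remove the reason to prespecify: the covariate is nearly free, and choosing it afterwards would be open to question.

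The objection that every correlation is assumed also stands. If the enrolment score is the first point of the AUC, which the documents do not say, r would be higher. The 4-week AUC (section 5.0) and the 8-week AUC (section 13.21) need not share the same r or SD.

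A last objection is that calling the unadjusted analysis valid says too much, because the model uses treatment received and section 13.2 replaces patients who leave before 2 weeks. That is a fair caution. Validity here concerns only the missing covariate and does not clear those separate matters.

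**Conclusion.** The concern holds, as a matter of efficiency. The primary model omits a baseline measurement of its own outcome item that every enrolled patient will have, and neither the prognostic list nor the randomisation makes up for it. Omitting it introduces no bias, and the stated 70% power is right.

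For assumed correlations of 0.2 to 0.4, adjustment gains about 0.5 to 5.5 points of power. It also protects the estimate from an expected shift of 9% to 18% of the target effect when the arms differ at baseline by one SE. If baseline proves unrelated to AUC, about 1 point of power is lost. These sizes rest on the assumed correlations and on the SD of 2.43 implied by section 13.1. The change should be made, but nothing in the plan is invalid without it.

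**What to change.** In section 13.2, state the primary model as AUC regressed on randomised arm and continuous baseline BFI worst fatigue, with the one-sided 5% test on the arm coefficient. Keep the unadjusted comparison as a sensitivity analysis. Report both the unadjusted and the baseline-adjusted SD for planning the later trial, and add baseline worst fatigue to the prognostic list.

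Using randomised arm follows the intent-to-treat rule in sections 5.0 and 13.23. It also replaces treatment received in the model, which is a separate point and should be recorded as such. The AUC window (4 weeks in section 5.0, 8 weeks in section 13.21) must likewise be reconciled separately; this change applies under either.

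The cost is a few sentences in the analysis plan, one degree of freedom, and at worst about 1 point of power. No new data are needed.
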